•**Assessments:** The primary dependent measures will be extracted from the Quantitative Sensory Testing for pain thresholds. Other assessments include: Brief Pain Inventory (BPI), the pain craving form, and subjective pain rating scales, delivered before and after TMS. Participants will also complete the Beck Depression Inventory (BDI-II), the Profile of Mood States (POMS), the Pittsburgh Sleep Quality Index (PSQI), the State-Trait Anxiety Inventory (STAI), and Barratt Impulsiveness Scale (BIS), which assesses anxiety and depression measures. Though these are not primary outcomes, the results will be used in post-hoc analyses of the data. All surveys will be filled out by the patient on tablet computers (Apple iPad/Microsoft Surface) and data entry will be done directly via Redcap Software. •**MRI scanning:** The MRI scanning session will last 30 minutes and will contain: 1) a high resolution anatomical image (T1-weighted MPRAGE (TR 1.9 sec, TE 2.26 ms, 2x GRAPPA, 1 mm isotropic)), 2) resting state functional connectivity (TA 7 minutes, voxel size: 2.5 x 2.5 x 2.5, TR = 2.6 s, TE = 25 ms, flip angle = 60°, FOV = 224 mm x 224 mm, matrix size = 64 x 64), **For each of the above strategies (Active rTMS or Active Sham) we will explore a**

series of SubAims designed to quantify the effects of rTMS on subjective pain, quantitative sensory testing, and brain reactivity to pain.

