SubAim 1: Evaluating Pain using Clinical Assessments Quantitative Sensory Testing (QST). Using the Medoc ATS thermal stimulator (Medoc Ltd Advanced Medical Systems, Ramat Yishai, Israel), 3 primary outputs will be compiled for each individual via the method of limits (54): sensory threshold, pain threshold, tolerance threshold. The thermode will be attached to the right forearm, and when the procedure begins it will begin heating from room temperature (32°C) at 0.2°C per second. Participants will indicate when they first detect the temperature change (sensory threshold), when it becomes painful (pain threshold), and when they can no longer tolerate the stimuli (tolerance threshold). When participants indicate tolerance, the operator will initiate rapid (>8°C per second) cooling. For safety, the thermode will be unable to exceed 51° and will initiate rapid cooling at that point. QST will be performed at two timepoints for each visit – prior to the initial MRI session and after the second MRI session. **Pain Questionnaire.** In order to evaluate current levels of pain, we will ask participants to rate their current level of pain and discomfort (scale, 0 through 10), each time the participant comes in (Table 1). On days where the individual receives rTMS, they will fill out this assessment before and after each session. **Pain and Craving Questionnaire:** In addition to the Pain Questionnaire above, participants will also rate their urge to use a pain reliever (Scale 0 – 10) and the amount they would be willing to pay for a pain reliever (In US Dollars). This questionnaire will be used at the same time during each intervention visit as the Pain Questionnaire (Table 2).

SubAim 2: Evaluating Pain using Neuroimaging Data At baseline we expect that people with chronic pain will have elevated activations in the Pain Network. This will be analyzed through the resting state connectivity network. Following sham stimulation, we do not anticipate a significant reduction of this response. Based on prior studies by our group in non-opiate dependent individuals, following LTP-like stimulation of the DLPFC, we expect a significant amplification of the DLPFC (% BOLD signal change), and a reduction of the Pain Network (dACC, anterior insula) reflecting the increased influence of executive processes. MPFC TMS however will likely not have as large of an effect on ECN engagement during the instruction to Control the pain.

Data Analysis Plan.

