A. Quantitative Sensory Testing. The QST pain assessment produces 3 output variables: sensory threshold, pain threshold, tolerance threshold (all expressed in degrees Celsius). The hypothesis will be tested using a within-subject repeated measures design (time x treatment) wherein time is the repeated variable and Real or Sham TMS is the grouping variable. Given that the purpose of this pilot study is to develop effect sizes for a subsequent R01, we will derive least-squares means effect sizes of this strategy on these thresholds. Secondary analyses will evaluate the relationship between QST levels and the neural response to pain, as well as the relationship between QST values and evoked cortical responses. Integrating these measures together will provide a more complete picture of how cortical activity is able to modulate the pain response.

B. Questionnaires and Evaluations. The Opiate Pain inventory produces 4 output variables of interest: level of discomfort, level of pain, urge to use opiates, amount willing to pay for an opiate. The hypotheses for the Aims will be tested using a within-subject repeated measures design (time x treatment) wherein time is the repeated variable and Real or Sham TMS is the grouping variable. Given that the purpose of this pilot study is to develop effect sizes for a subsequent R01, we will derive least-squares means effect sizes of our research strategy on these 4 variables, to determine the unique contributions of this intervention.

C. Neuroimaging Data (Aim 2): Immediately following acquisition, functional structural data will be uploaded to a secure data server and converted to NIfTI format. All preprocessing and analyses will be

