A. Quantitative Pain Testing. Based on our pilot data, we expect an interaction between treatment (Real DLPFC or MPFC TMS vs. Sham) and time (Before vs. After rTMS) on the painfulness QST measure but no effect on sensory or tolerance levels. Alternative outcomes: It is possible that individuals will experience a small level of acute pain relief from their normal regimen of medication. We will be collecting information on opiate dose and timing at each visit to be used as potential covariates. Further, there is the possibility that pain tolerance will rise, possibly also reflecting improvements in executive function.

B. Qualitative Pain Assessment. We expect reductions in pain and discomfort when comparing active vs sham. However, based on prior data in opiate dependent individuals, we expect the effect size of DLPFC rTMS in to improve measures of Control but not measures of mood, whereas MPFC will have a larger effect on mood.

C. Neuroimaging. At baseline we expect that there will be elevated activations in the Pain Network in individuals with chronic pain. Following sham stimulation, we do not anticipate a significant reduction of this response. Based on prior studies by our group in non-opiate dependent individuals, following LTP-like stimulation of the DLPFC, we expect a significant amplification of the DLPFC (% BOLD signal change), and a reduction of the Pain Network (dACC, anterior insula) reflecting the increased influence of executive processes. MPFC TMS however will likely not have as large of an effect on ECN engagement during the instruction to Control the pain.

Alternative outcomes: Though pilot data suggest that a single treatment will acutely reduce self-reported pain, it is possible that the neural circuits in opiate dependent individuals do not have the same 'plasticity potential' as in controls. The results of the baseline cortical modulation assessment of pain (instruction to "control" the pain) will help resolve this alternative outcome. If we fail to replicate prior work showing DLPFC activation, this could reflect executive deficits (58), suggesting that the MPFC TMS will be more efficacious.

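### To the extent that participants reach the 51 °C safety limit, heat tolerance is right-censored, and the planned least-squares means would understate a real-versus-sham rise

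*Combined protocol and SAP*

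**What the plan says.** All references are to section 10.0 of the combined protocol and SAP.

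- **SubAim 1** describes the heat test. On the ramp it says "it will begin heating from room temperature (32°C) at 0.2°C per second". On the ceiling it says "For safety, the thermode will be unable to exceed 51" degrees, and that the device then cools rapidly by itself. It also says that "3 primary outputs will be compiled for each individual via the method of limits (54): sensory threshold, pain threshold, tolerance threshold".
- **Assessments** gives a narrower emphasis: "The primary dependent measures will be extracted from the Quantitative Sensory Testing for pain thresholds".
- **Data Analysis Plan, A** puts the three outputs on one continuous scale: "sensory threshold, pain threshold, tolerance threshold (all expressed in degrees Celsius"). They are analysed by a time-by-treatment repeated-measures design with real or sham TMS as the grouping variable, and "we will derive least-squares means effect sizes of this strategy on these thresholds". The stated purpose is to supply effect sizes for a later grant application. Whether these are in degrees or standardised is not stated.
- **Expected Outcomes, A** predicts an effect on painfulness and none on sensory or tolerance levels. Under alternative outcomes it adds that "there is the possibility that pain tolerance will rise".

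No section says what is recorded when 51 °C is reached without a tolerance response, plans a count of such readings, or names a method for censored data. No mean, SD or expected share at the cap is given for tolerance.

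**The concern.** A reading that ends because the device cools itself is not a measured tolerance; it is a lower bound. If it enters the model as 51, part of any rise is cut off, and more is cut off in the arm with the higher tolerance. The difference in mean tolerance is then pulled towards zero.

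Two things are at stake. The tolerance effect size is one of the quantities that the pilot is meant to pass on. And because no effect on tolerance is predicted, a null result would look like confirmation. Without a count at the cap, it could not be told apart from a ceiling artefact.

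**Working it through.** **Plan's own figure.** There is none on this point. The only power statement (Sample size estimate: n=15, 80% power, effect sizes 0.70 to 1.08) rests on fMRI data and does not bear on the heat test.

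**Inputs from the documents.** Start 32 °C, ramp 0.2 °C per second, cap 51 °C. The cap is reached after (51 − 32)/0.2 = 95 seconds.

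**Assumptions, not in the documents.** Latent tolerance is normal with equal SD in both arms; the true real-minus-sham shift is 0.70 latent SD; readings at the cap are scored 51; the share of sham readings at the cap runs from 0 to 40%.

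**Formula.** In SD units with sham mean 0, the cap sits at c, where Φ(c) = 1 − share of sham at the cap. For an arm with mean μ, put a = c − μ. The expected recorded mean is

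μ·Φ(a) − φ(a) + c·(1 − Φ(a)).

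**Worked case, 20% of sham at the cap.**

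1. c = 0.842.
2. Sham: 0 − 0.280 + 0.842 × 0.200 = −0.112.
3. Active, a = 0.142: 0.70 × 0.556 − 0.395 + 0.842 × 0.444 = 0.368.
4. Raw difference: 0.368 + 0.112 = 0.480, or 69% of 0.70.
5. The recorded SDs also shrink, to 0.833 (sham) and 0.632 (active). Pooled 1:1, √((0.833² + 0.632²)/2) = 0.739, so the standardised effect is 0.480/0.739 = 0.65, or 93% of 0.70.

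| Sham at cap | Active at cap | Raw difference (latent SD) | Share of 0.70 | Effect by observed SD (1:1) | Share of 0.70 |
|---|---|---|---|---|---|
| 0% | 0% | 0.70 | 100% | 0.70 | 100% |
| 1% | 5% | 0.68 | 97% | 0.70 | 100% |
| 5% | 17% | 0.63 | 90% | 0.69 | 99% |
| 10% | 28% | 0.57 | 82% | 0.68 | 97% |
| 20% | 44% | 0.48 | 69% | 0.65 | 93% |
| 30% | 57% | 0.40 | 57% | 0.61 | 88% |
| 40% | 67% | 0.32 | 46% | 0.58 | 82% |

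Weighting the SD by 32 real and 16 sham gives 0.70, 0.68, 0.65 and 0.62 in the last four rows.

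**Change scores.** The planned design is before-and-after, so this was simulated with an assumed latent SD of 2 °C, a true rise of 1.0 °C (0.5 SD) and a before-after correlation of 0.7. The uncensored effect is 1.0/(2 × √(2 × (1 − 0.7))) = 1.0/1.549 = 0.65. With 20% of sham readings at the cap, the raw difference is 0.72 °C and the standardised effect 0.55. Power for 32 versus 16 falls from 54% to 42%.

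**If capped readings were dropped instead of scored 51** (same SD and rise), the 1.0 °C difference becomes 0.90, 0.64, 0.51 and 0.43 °C at 1, 10, 20 and 30% of sham at the cap. The direction is the same and the loss larger.

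**Does the remedy work?** A right-censored (Tobit) fit to the simulated post-treatment values gave median estimates of 0.94 to 1.09 °C against the true 1.0, over 0 to 50% at the cap.

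**The case against.** The strongest reply is that the problem may not arise. The documents give no tolerance distribution, and if nobody reaches 51 °C the loss is zero. With an assumed sham mean of 46 °C, SD 1.5 and a 1 °C rise, it is 0.2%. This stands, and it is why the point is conditional. A reader might infer that any rise in tolerance will be understated; the documents do not support that.

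Four further inferences are tempting and should not be drawn.

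- **That the effect size for the next trial falls to about half.** The 46% applies to the raw difference in latent SD units at 40% of sham at the cap. A standardised effect uses the observed SD, which shrinks too, and the loss is then much milder. The plan does not say which scale it will report.
- **That the plan scores capped readings as 51.** It does not say so. The supportable gap is that the recording rule is missing. Scoring at 51 and dropping both bias the difference towards zero.
- **That the standard error would be too small.** Nothing here shows that; it describes the spread of the recorded readings.
- **That the main outcome is compromised.** Assessments stresses pain thresholds, and the predicted effect is on painfulness. Pain threshold would be touched only if someone reported no pain by 51 °C.

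It can also be said that a Tobit mixed model is heavy for a 48-person pilot and adds a normality assumption. That is fair, and it is a reason to keep the plain means beside it. The flag and the count do not depend on the model.

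**Conclusion.** The point holds in conditional form and is minor. The cap right-censors tolerance by design, the planned least-squares means ignore this, and where readings reach the cap the real-versus-sham difference is biased towards none. Tolerance is a named output with an effect size to be carried forward, but it is not the hypothesised effect.

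The size cannot be fixed from the documents. It runs from nothing, if no one reaches 51 °C, to a raw loss of about a third at 20% of sham at the cap (0.70 to 0.48) and more than half at 40%. At 20%, the standardised loss is about 7% cross-sectionally (0.70 to 0.65) and about 15% on change scores (0.65 to 0.55). These figures assume normality, equal latent SDs and scoring at 51. The 0.70 shift, like the 0.5 SD shift and the 0.7 correlation behind the change-score figure, is illustrative and not a heat-test estimate.

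**What to change.** Leave the 51 °C safety limit as it is; nothing here questions it.

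1. State what is recorded when the limit is reached, and set a flag at the time of testing when heating ended without a tolerance response. It must be prospective, because a stored 51 may not later distinguish a response from a cut-off.
2. Report the number and share of flagged readings by arm and visit.
3. Analyse tolerance with a right-censored (Tobit) mixed model, with the planned least-squares means alongside.
4. State whether the effect sizes are in degrees or standardised.

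The cost is one data field, a slightly more complex model for one output, and reliance on normality above the cap. If the count is zero, the censored model reduces to the ordinary one and nothing is lost.

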Participants. We will enroll 48 men and women 18-75 years old with CLBP that have a history of current prescription opioid use (>3 months) for the treatment of pain. Participants will be recruited through the community along with MUSC clinics. Patients that have previously agreed to be contacted for research and have current chronic pain will be referred to the study. Our prior history with targeted enrollment (See Significance) indicates this is feasible within 20 months, leading to full completion by 22 months. **Exclusion criteria:** Typical MRI and TMS exclusionary criteria, including metal above the neck or implanted in the body, use of prescription medications that lower seizure threshold, a history of seizures or traumatic brain injury, pregnancy or trying to become pregnant, current substance use or dependence (other than opioids and nicotine), history of seizure disorder, and claustrophobia. Participants will provide written informed consent following explanation of the study. **Sample size estimate:** A power estimate for Aim 1 and 2 was prepared using an original fMRI dataset previously collected in our laboratory (8). In this experiment, 18 healthy controls performed the same fMRI pain paradigm as the present study before and after a single session of 10 Hz rTMS. Mean parameter estimates for the “heat pain vs. rest” condition were extracted from several *a priori* regions of interest. These data yielded an effect size which ranged from 0.70 (thalamus) to 1.08 (insula) (n=15 yields 80% power using a two-sided p<0.05). Allowing for a 10% dropout rate after the screening visit, and up to a 20% dropout rate at the end of the Treatment phase (Week 4), as well as a 10% data loss rate for MRI (Aim 2) due to individuals with excessive head motion in the MRI scanner, screening 58 individuals should lead to complete data from 48 individuals (16 real DLPFC, 16 real MPFC, 16 sham (50% at each site)). Randomization will be handled by the MUSC data coordination center of the Biostatistical Unit ([name], biostatistician) and a Latin Square design with replacement will be used to ensure even enrollment across groups with replacement.

General Methods

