All key personnel will undergo appropriate IRB training for dealing with human participants and will be trained by the PI in all aspects of the study interventions. Personnel listed in this protocol (as well as any rotating medical students, graduate students, psychiatry residents or fellows that may be exposed to this investigation as part of their research training exposre) will be required to maintain their certification of HIPPA training and Protection of Human Participants in Research training on an annual basis. Any new personnel without experience in human clinical research will be encouraged to attend the MUSC Core Clinical Research Training Course, which is offered live and online throughout the year. Through these measures we will ensure that all study staff will be trained and will maintain ongoing understanding of research ethics and the rights of the participant during the consenting process and throughout an individual's participation in the study.

Data analysis plan:

Data for this study (behavioral assessments, functional MRI measurements) will be acquired by the members of the [name] lab, including graduate students and research specialists. These individuals will also perform data under the guidance of the PI. Manuscript composition will be led by the PI, with the assistance of the research team.

Quality assurance plan:

The PI has weekly meetings with the research team to discuss qualitative comments received during data collection and any problems in data collection. Initial data analyses will examine distributions of variable scores, and comparability of baseline characteristics across conditions in case analyses need to be adjusted for these. Confidentiality protections are outlined below.

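### The QST and questionnaire analyses do not adjust for the outcome's own baseline value, and other adjustment is left open to an unspecified look at baseline comparability

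*Combined protocol and SAP*

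**What the plan says.** Section 10.0, Data Analysis Plan, part A (QST thresholds) and part B (questionnaires) both use a "within-subject repeated measures design (time x treatment", with real or sham stimulation as the grouping variable. Neither part names a covariate. Both say that the aim is least-squares-means effect sizes for a later grant. The QST paragraph of Expected Outcomes gives time two levels, before and after rTMS, so the baseline value enters as part of the outcome. The Assessments paragraph takes the primary dependent measures from QST.

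Separately, the Quality assurance plan in Section 13.0 says that initial analyses will examine "comparability of baseline characteristics across conditions in case analyses need to be adjusted for these". It names no variables, threshold or resulting model.

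Other covariates appear elsewhere in Section 10.0 without a link to balance:
- the number of sessions received, for early dropouts;
- the time from stimulation to assessment, and scalp-to-cortex distance;
- sex, depression score and duration of opiate use, as an exploratory analysis;
- opiate dose and timing, as possible covariates.

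None of these is the baseline value of the outcome being analysed.

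**The concern.** With one value before and one after, the ordinary time-by-treatment interaction is algebraically a two-sample comparison of change scores. Subtracting the whole baseline is optimal only when the regression slope of follow-up on baseline is 1. With equal variances that slope is the correlation r, so a change score over-corrects. Estimating the slope recovers the lost precision.

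The comparability clause raises a second issue. Under randomisation, observed baseline differences arise by chance, so they are a poor guide to which covariates to use. Prognostic value is the better guide. A clause with no variables and no threshold leaves the analyst free to choose a model after seeing data.

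Both matter because the trial is small and its stated product is a set of effect sizes. Their precision, and how they were selected, carry straight into the next trial's sample size.

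**Working it through.** **The plan's own power figure.** Section 10.0 says "n=15 yields 80% power using a two-sided p<0.05", for "an effect size which ranged from 0.70 (thalamus) to 1.08 (insula". A two-sample t-test at 1.08 needs 15 per arm (power 81.5%), so the figure reproduces at the top of the range. At 0.70 it does not: power with 15 is 45.7% for a two-sample test and 71.3% for a paired test. These effect sizes are fMRI estimates from healthy volunteers before and after a single session. They are used below only as illustrative differences.

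**Inputs.** Group sizes are "16 real DLPFC, 16 real MPFC, 16 sham (50% at each site", so 16 v 16 for one active arm against sham, or 32 v 16 if the real arms are pooled, as the real-or-sham grouping variable implies. Alpha is two-sided 0.05. The documents do not give r, so 0.3 to 0.8 is assumed.

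**Variance of the arm contrast.** With one value before and one after, and equal variances (follow-up variance set to 1):
- Post-only: 1
- Change score: 2(1 − r)
- Baseline-adjusted (ANCOVA): 1 − r²
- Ratio of ANCOVA to change score: (1 − r²)/[2(1 − r)] = (1 + r)/2, a reduction of (1 − r)/2

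Estimating one slope from N = 32 normally distributed observations multiplies the ANCOVA variance by 1 + 1/(N − 4) = 1 + 1/28 = 1.036. At r = 0.7, for example, 0.85 × 1.036 = 0.880, a 12% reduction.

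| r | Change score | ANCOVA | Reduction, large sample | Reduction, 16 v 16 |
|---|---|---|---|---|
| 0.3 | 1.40 | 0.91 | 35% | 33% |
| 0.5 | 1.00 | 0.75 | 25% | 22% |
| 0.7 | 0.60 | 0.51 | 15% | 12% |
| 0.8 | 0.40 | 0.36 | 10% | 7% |

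At 16 v 16 the two methods break even where 1.036(1 + r)/2 = 1, that is r of about 0.93.

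**Power at an assumed difference of 0.70 SD of the outcome.** Noncentral t, with ANCOVA charged one degree of freedom. Values are change score to ANCOVA, before the slope-estimation cost.

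| r | 16 v 16 | 32 v 16 |
|---|---|---|
| 0.3 | 37% to 52% | 47% to 65% |
| 0.5 | 48% to 60% | 61% to 73% |
| 0.7 | 70% to 76% | 82% to 88% |

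With the slope-estimation cost included, the ANCOVA powers at 16 v 16 are 50%, 58% and 75%.

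**Cost of unrelated covariates.** With three covariates the factor is 1 + 3/(N − 6) = 1 + 3/26 = 1.115. If the two beyond baseline are unrelated to outcome, the reductions at 16 v 16 become 27.5%, 16% and 5% at r = 0.3, 0.5 and 0.7. At r = 0.8 the gain is gone (0.90 × 1.115 = 1.004).

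**Type I error of data-driven adjustment.** 100,000 simulated null trials at each r, 16 v 16, results for r = 0.3 / 0.5 / 0.7:
- Fixed rule (ANCOVA if baseline differs at p < 0.05, otherwise change score): 0.042 / 0.043 / 0.046
- Smaller of the two p-values: 0.078 / 0.073 / 0.068
- Change-score test, only in trials with a significant baseline difference: 23% / 17% / 13%

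The chance that at least one of k independent baseline variables differs at 0.05 is 1 − 0.95^k: 14% for k = 3 and 34% for k = 8. The clause would therefore be triggered fairly often.

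**The case against.** Much can be said for the plan.

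- **The baseline is used.** A reader might infer that it is wasted. It is not: it is a level of the time factor, and for r above 0.5 the planned test is more precise than a post-only comparison, since 2(1 − r) is then below 1.
- **The model form is not fully stated.** A mixed model with baseline means constrained equal would also fit the wording and would largely remove the loss. This stands, and it makes the fault partly one of underspecification. But nothing in the documents states that constraint, and the ordinary reading is the change-score one.
- **Covariates are named elsewhere.** A reader might infer that adjustment depends only on balance. The documents contradict that, and the exploratory set is chosen for documented influence on pain. Even so, none is the outcome's own baseline. Sessions received, time from stimulation to assessment and visit-level opiate dose are recorded after randomisation. The rest of the list is largely exploratory or optional.
- **The comparability clause is a contingency in a quality-assurance paragraph.** A reader might infer that it inflates type I error. A fixed rule did not do so in simulation, and nowhere is it proposed to pick the smaller p-value. What stands is that the clause leaves room for choice.
- **This is a pilot, and both estimators are unbiased under randomisation.** True, so the issue is precision. Precision still matters when the product is an effect size for planning.

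**Conclusion.** The point holds as an improvement to the analysis, not as an error that invalidates it. As written, parts A and B describe a change-score comparison, and adjusting for the baseline already collected would be more precise at 16 v 16 for any r below about 0.93. The gain shrinks as r rises: about 33% of the variance at r = 0.3, down to 7% at 0.8.

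The variance ratios rest on the assumed r, on equal variances at the two times and on one value before and one after. The power figures also rest on a 0.70 SD difference that is not a QST figure, so they show scale only.

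On the comparability clause, the supported conclusion is that the model is left open to discretion, with error of about 7–8% in the worst case examined. Actual inflation is not shown.

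**What to change.** 1. For each QST threshold and questionnaire score, model post-baseline values by arm, visit and arm-by-visit, adjusted for that measure's baseline value (ANCOVA or MMRM). A repeated measures model with baseline means constrained equal across arms is an acceptable alternative. State which form is used, the visit at which the contrast is read, and whether the real arms are pooled.
2. Delete the clause in the Section 13.0 Quality assurance plan that links adjustment to observed comparability. Baseline tables can stay as description.
3. Prespecify any further covariate only if it is measured before randomisation and expected to be prognostic. Unrelated covariates cost precision at this sample size.

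Items 1 and 2 need only SAP wording and no new data. The cost of item 1 is one estimated slope per outcome, already included in the 16 v 16 figures. Item 3 is not free unless the covariates are prognostic.
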